8.8.2 Clinical Laboratory Evaluation

Clinical laboratory variables will be summarized using descriptive statistics for baseline, post-baseline, and change from baseline to post-baseline values.

All lab parameters will be summarized by worst grade/value by cycle in addition to overall worst grade/value. Lab cycles are windowed as a cycle's start date until the next cycle's start date. See Appendix 2 Visit Windowing.

Table 3: Lab Unit Conversions

Lab Test	Standard Unit	%	g/dL	/uL	'K/mol' or 'x10^3/mol'
HGB	g/L		Value*10		TBD
Lymphocytes	10^9/L	(Value*WBC)/100		value*0.001	
Neutrophils	10^9/L	(Value*WBC)/100		value*0.001	
Platelets	10^9/L			value*0.001	
WBC	10^9/L			value*0.001	

The following units were considered equivalent to 10^9/L: '10**3/uL', '10*3/UL', 'x10^3/mm^3', 'x10^3/microL', 'K/UL', 'x10^9/L', 'K/mm3', '10*9/L', 'K/mol', 'x10^3/mol'

Table 4: CTCAE Grading

PFIZER CONFIDENTIAL

Lab Test	Normal		CTCAE Grade			
			1	2	3	4
HGB	\geq LBLLN and \leq LBULN	High	$> 0 - 1.2412$ mmol/L above LBULN	$>1.2412 -$ 2.4824 mmol/L above LBULN	> 2.4824 mmol/L above LBULN	
		Low	$< LBLLN - 6.2$ mmol/L	$< 6.2 - 4.9$ mmol/L	< 4.9 mmol/L	
Lymphocytes	\geq LBLLN and \leq 4.0	High		$4 < to \leq 20$	> 20	
		Low	$0.8 \leq to <$ LBLLN	$0.5 \leq to < 0.8$	$0.2 \leq to < 0.5$	< 0.2
Neutrophils	\geq LBLLN	Low	$< LBLLN - 1.5$ $X 10^9/L$	$< 1.5 - 1.0 X$ $10^9/L$	$< 1.0 - 0.5 X$ $10^9/L$	$< 0.5 X 10^9/L$
Platelets	\geq LBLLN	Low	$< LBLLN -$ $75.0 X 10^9/L$	$< 75.0 - 50.0 X$ $10^9/L$	$< 50.0 - 25.0 X$ $10^9/L$	$< 25.0 X$ $10^9/L$
WBC (leukocytes)	\geq LBLLN and $<100 X 10^9/L$	High			$>100 X 10^9/L$	
		Low	$< LBLLN - 3.0$ $X 10^9/L$	$< 3.0 - 2.0 X$ $10^9/L$	$< 2.0 - 1.0 X$ $10^9/L$	$< 1.0 X 10^9/L$

ANALYSES OF QUALITY OF LIFE ENDPOINTS

All analyses will be conducted using the QoLAS. Where noted, the following binary categorizations will apply: age at baseline (<70 years and and \geq 70 years), LOT (1 line and \geq 2 lines), ECOG performance status (0 and 1-5), any dose modifications (yes and no), and SAE status (none and \geq 1). Also, binary categorizations for ADL (all activities “No Assistance Needed” and other) and G8 index score (\leq 14 and $>$ 14) will be created.

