4. Physician MBC Treatment Selection Survey: Treating physicians will complete a treating physician MBC treatment selection survey that will capture the reason(s) for treatment choice at start of palbociclib therapy and at start of subsequent therapies.

5. Clinical assessments: overall clinical response as judged by treating physician, at intervals per standard of care schedule: imaging assessment, clinical progression, and clinical biomarkers.

CCI

7. CBC: Baseline and during palbociclib treatment, enter any CBC during the 1st 3 cycles, then enter Day 1 (or prior to start of a new cycle) CBC for the subsequent cycles as per standard of care.

8. AE/SAE reporting begins at the time of the patient's first dose of palbociclib or the time of the patient's informed consent if s/he is already exposed to palbociclib and up to 28 calendar days following the last administration of palbociclib.

Table 2: EORTC QLQ-C30 and Geriatric Assessments

Data Collection and Entry	Baseline	Through End of Treatment with Palbociclib
	SOC Visit 1	
EORTC QLQ-C30 ¹	x ¹	x ¹
G8 Screening Tool ²	x ²	x ²
ADL: Activities of Daily Living ²	x ²	x ²

ADL = Activities of Daily Living; EORTC QLQ-C30 = European Organisation for the Research and Treatment of Cancer Quality of Life Questionnaire Core 30

1. EORTC QLQ-C30 will be collected at baseline (before starting palbociclib) then monthly for the first 3 months of treatment with palbociclib, then every three months until the end of treatment with palbociclib.

2. G8 Screening Tool and Activities of Daily Living to be completed only for patients equal to or greater than 70 years of age at the time of study enrollment. G8 and ADL will be collected at baseline (before starting palbociclib) then monthly for the first 3 months of treatment with palbociclib, then every three months until the end of treatment with palbociclib. ADL to be completed by the patient or in conjunction with the appropriately delegated site staff, G8 to be completed by the treating physician or the appropriately delegated site staff.

PFIZER CONFIDENTIAL

STUDY OBJECTIVES

The objectives of this prospective NIS of palbociclib in ABC treatment are:

- Palbociclib prescribing and treatment patterns in routine clinical practice in ABC treatment;
- Clinical outcomes;
- MBC treatment sequence prior to, during, and after palbociclib ;

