8 STATISTICAL ANALYSIS

This study has a convenience sample; thus, results may not be generalizable to the entire population with the disease. Due to the study's exploratory nature, study measures will be summarized descriptively. Furthermore, any p value reporting should be placed in a descriptive framework for hypothesis generation and any such inferential analysis is intended to guide further research.

All analyses will be conducted using SAS® version 9.4 or higher.

The intention is to analyze all available data. In the advent that COVID may cause gaps in subject data or require adjustments to statistical methodologies, our intent is to address such issues if or as needed. Both ICON and Pfizer have internal guidances and recommendations on file to assist with decision-making with regards to COVID-related data issues and these will be consulted if or as needed.

GENERAL METHODS

For continuous variables, means, standard deviations (SD), medians, minimums, maximums, and missing will be reported. For discrete variables, frequencies and percentages will be reported. Missing or unknown categories for each variable also will be presented. Percentages will be calculated excluding missing or unknown values. 95% Confidence Intervals (CI) are two-sided.

All summaries will be performed for all patients in the corresponding analysis set and by treatment combination defined at study entry within the corresponding analysis set:

- Palbociclib + Letrozole or Anastrozole
- Palbociclib + Fulvestrant
- Palbociclib + Exemestane
- Other

The baseline record is defined as the last observed measurement prior to palbociclib administration. Change from baseline is defined as the post-baseline value minus the baseline value.

Time in days between two dates will be calculated using the formula most recent date minus earlier date plus 1. For time in months, the same formula for days will be applied but then divided by 30.4. For time in years, the same formula for days will be applied but then divided by 365.25.

Variable definitions are found in Appendix 1 Data Derivation Details.

DISPOSITION OF SUBJECTS

A subject disposition summary will be reported. Subjects' study completion date and reason for premature termination will be reported in listing format. Number of subjects with initial diagnosis and with recurrent diagnosis will be reported in table and listing format.

DEMOGRAPHIC AND BASELINE CLINICAL CHARACTERISTICS

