8.8.1 Adverse Events

All safety analyses will be completed following Pfizer safety analysis standards, including descriptive statistics on all safety endpoints for the FAS. AEs will be monitored throughout the study duration. If the type and/or number of AEs warrants further examination, interim analyses will be conducted to determine whether those experiencing AEs are systematically different from other study participants. If the percentage of patients withdrawing from the study exceeds 25%, interim analyses will be conducted to examine whether systematic differences exist between those withdrawing from the study and those that continue with palbociclib treatment. Descriptive statistics comparing women and men who complete follow-up with those who withdraw from the study will also be completed to determine whether there are any systematic (demographic, clinical) differences between these such defined groups.

Descriptive statistics will be presented for all AEs and will be examined by AE grade. The incidence of all-cause and treatment-related AEs and SAEs separately will be reported. Specifically, a summary of incidence will be presented for the following variables:

- Patients evaluable for AEs
- Number of AEs
- Patients with AEs

PFIZER CONFIDENTIAL

- Patients with SAEs
- Number of SAEs
- Patients with Grade 3 or 4 AEs
- Patients with Grade 5 AEs
- Patients permanently discontinued study associated with AEs
- Patients permanently discontinued study associated with SAEs
- Patients permanently discontinued treatment associated with AEs
- Patients permanently discontinued treatment associated with SAEs
- Patients temporarily discontinued treatment associated with AEs
- Patients temporarily discontinued treatment associated with SAEs
- Patients with dose reduction associated with AEs
- Patients with dose reduction associated with SAEs
- Deaths

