APPENDIX 2: LAB VISIT WINDOWING

Visit	Visit Day	Window of Days	
		non-lab domains	CBC Labs
Baseline	1	<=1	
Day 15	15	n/a	2-18
Day 21	21	n/a	19-25
Day 28	28	n/a	26-45
Month 1	30	2-45	n/a
Month 2	60	46-75	
Month 3	90	76-135	
Month 6	180	136-225	
Month 9	270	226-315	
Month 12	360	316-405	
Month 15	450	406-495	
Month 18	540	496-585	
Month 21	630	586-675	
Month 24	720	676-765	
Month 27	810	766-XX	

If multiple records are assigned per analysis visit, the latest record will be selected for reporting.

An alternate presentation of lab data will display by Cycle. Cycle x is defined as any lab record between Cycle x start date until Cycle $x+1$ start date.

PFIZER CONFIDENTIAL

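### The Cycle 1 lab window has no pre-dose exclusion, so one Day 1 CBC can be both the baseline record and the worst grade; lab grades are also not linked to baseline grade

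*SAP*

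**What the plan says.** - **Worst grade (SAP 8.8.2):** "All lab parameters will be summarized by worst grade/value by cycle in addition to overall worst grade/value". No restriction to post-dose records is stated.
- **Cycle window (SAP 8.8.2):** "Lab cycles are windowed as a cycle's start date until the next cycle's start date". Appendix 2 repeats this for its alternate display: "Cycle x is defined as any lab record between Cycle x start date", running to the start of the next cycle. Neither place mentions time of dose.
- **Baseline (SAP Section 8, General Methods):** "The baseline record is defined as the last observed measurement prior to palbociclib administration".
- **Collection (SAP Table 1, footnote 7):** "CBC: Baseline and during palbociclib treatment, enter any CBC during the 1st 3 cycles". For later cycles, the count from Day 1 or just before the cycle is entered.
- **Link to baseline (SAP 8.8.2):** lab variables get descriptive statistics for "baseline, post-baseline, and change from baseline to post-baseline values". This concerns values. No cross-tabulation of baseline grade with later grade appears in 8.8.2, 8.9.6 or the appendices.
- **Breakdown (SAP Section 8, General Methods):** "All summaries will be performed for all patients in the corresponding analysis set and by treatment combination defined at study entry".
- **Standards (SAP 8.8.1):** "All safety analyses will be completed following Pfizer safety analysis standards". Those standards are not reproduced. Detail for the neutropenia analyses in 8.9.6 is left to a separate planning document.

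**The concern.** There are two gaps, one of definition and one of content.

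First, a count taken before any palbociclib can enter a table that readers will take to describe what happened on palbociclib. If it is the worst count of Cycle 1, or the only one, the patient's Cycle 1 grade is a pre-treatment grade. Nothing stated keeps the same record out of the overall worst grade.

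Second, this study has no control arm, so each patient's own baseline is the main reference for change. A patient with Grade 1 anaemia before and throughout treatment appears in the worst-grade table exactly as a patient who developed it on treatment. Change in mean value, even by hormonal partner, hints at movement but does not give the share of patients whose grade rose. Two groups that start with different baseline grades could look different on treatment although equal shares worsened.

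Low-grade anaemia and lymphopenia are where this matters. No estimand, error rate or sample size depends on it.

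**Working it through.** The plan states no figure to reproduce. The check applies the written rules to dated counts and then sizes the effect under declared assumptions.

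**Step 1: apply the rules.** Assume first dose on Day 1, which is also the start of Cycle 1, and 28-day cycles.

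| CBC drawn | Visit-window display (Appendix 2) | By-cycle display |
|---|---|---|
| Day before first dose | Baseline | none |
| Day 1, before the dose | Baseline | Cycle 1 |
| Day 15 | Day 15 | Cycle 1 |

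Only the Day 1 pre-dose count takes two roles. In the visit-window display a Day 1 count belongs to Baseline and post-baseline CBC windows open on Day 2, so that display is not part of this point. A count drawn on an earlier day is unaffected.

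**Step 2: size of the overlap.** The documents give no baseline prevalence of abnormal counts, so every input here is an assumption:

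- p = share of patients graded at baseline
- s = share of those still graded on post-dose counts alone
- h = share of patients ungraded at baseline who become graded

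Any-grade share with the pre-dose count: A1 = p + (1−p)h. Without it: A0 = ps + (1−p)h. The overlap adds A1 − A0 = p(1−s). This is an upper bound, reached only if every baseline count is drawn on Cycle 1 Day 1.

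| p | s = 95% | s = 90% | s = 80% |
|---|---|---|---|
| 5% | 0.25 points | 0.5 | 1 |
| 20% | 1 | 2 | 4 |
| 40% | 2 | 4 | 8 |

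With the planned 1,500 patients, the corners are 1,500 × 0.0025 = 3.75, about 4 patients, and 1,500 × 0.08 = 120 patients.

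**Step 3: what the worst-grade table cannot show.** Let g = share of those graded at baseline whose grade rises. The share who worsened is W = pg + (1−p)h, so A1 − W = p(1−g) = p(1−s) + p(s−g). With p = 20%, g = 30%, s = 90%: 14.0 points = 2.0 from the overlap + 12.0 from the missing link to baseline grade. The 12.0 is a difference between two legitimate quantities, any grade and worsened grade. It is not an error in the table.

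**Step 4: two groups.** Take p = 10% and 30%, with g = h = 30% in both and s = 90%.

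| Quantity | Group 1 | Group 2 | Gap |
|---|---|---|---|
| W | 0.03 + 0.27 = 30% | 0.09 + 0.21 = 30% | 0 |
| A1 | 0.10 + 0.27 = 37% | 0.30 + 0.21 = 51% | 14 points |
| A0 | 0.09 + 0.27 = 36% | 0.27 + 0.21 = 48% | 12 points |

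Removing the overlap takes away 2 of the 14 points and 12 remain. Only a table that conditions on baseline grade shows that the two groups worsened equally.

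**Step 5: Grade 3/4 neutropenia.** The overlap cannot exceed the share with Grade 3/4 at baseline. If that is at most 1% (assumed), the effect is at most 1 point. Protocol 6.2 reports 62.0% Grade 3/4 neutropenia on palbociclib plus fulvestrant in PALOMA-3.

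**The case against.** **The SAP already separates baseline from treatment.** It defines the baseline record, 8.8.2 names baseline and post-baseline apart, and Table 1 has separate columns for baseline and for the treatment period. A careful programmer would probably leave the baseline record out of Cycle 1. That is fair and makes this a drafting gap. But the written cycle window takes in every record from the start date, and a by-cycle program written to it would include the pre-dose count.

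**The sponsor's standards may already call for a grade shift table.** The sentence in 8.8.1 covers all safety analyses, and those standards cannot be seen. This stands. A reader might infer that no baseline-by-worst-grade table will be produced; the documents show only that 8.8.2 does not print one. The second change below is therefore conditional. Nothing cited indicates that the standards alter the cycle window.

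**Clinically relevant cytopenias are captured elsewhere.** AEs are reported by grade and relatedness, and Protocol Section 10 makes an abnormal result an AE when, for example, it causes symptoms or changes dosing. This stands for the important events. It leaves asymptomatic low-grade change, which is what a grade table is for. The SAP makes this within-patient comparison elsewhere: it defines worsening from baseline for the EORTC QLQ-C30 and allows paired tests of ADL and G8 categories.

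**The study is descriptive.** True, and it limits the weight of the point. A description should still keep pre-treatment records out of treatment cycles.

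**Conclusion.** The point holds as a minor one. Read literally, the rules let a pre-dose Cycle 1 Day 1 CBC be both the baseline record and a Cycle 1 or overall worst grade. How often it would change a patient's grade is unknown. The bound p(1−s) runs from 0.25 to 8 points for p of 5% to 40% and s of 95% to 80%, and assumes that every baseline count is drawn on Cycle 1 Day 1.

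It is also true of the printed text that values, but not grades, are linked to baseline. Whether that gap is real depends on sponsor standards that are not in the documents.

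A reader might go further and infer that the worst-grade table overstates palbociclib's haematological toxicity by p(1−g), 14 points in the worked example. The documents do not support that. The SAP calls the table a summary of worst grade and never describes it as treatment-emergent or as worsening, so p(1−g) measures information the table does not give. Only p(1−s) measures double use of a record. Nor should the point be carried over to Grade 3/4 neutropenia, which is little affected.

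**What to change.** **1. Cycle window (SAP 8.8.2 and Appendix 2).** Add one sentence: counts taken before the first palbociclib dose are excluded from Cycle 1 and from overall worst grade, and a count dated on the first-dose day with no recorded time is treated as baseline.

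**2. Grade shift table (SAP 8.8.2), unless the sponsor's safety standards already require it.** For haemoglobin, lymphocytes, neutrophils, platelets and WBC, tabulate baseline grade against worst post-dose grade in the low direction. Show it overall and, if wanted, by hormonal partner. Report the share whose grade rose among patients with both values, and give patients with no pre-palbociclib CBC a separate row. Keep the worst-grade table.

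**Cost.** The first change is wording only. The second uses CBCs already collected: five panels overall, or 5 × (1 + 4) = 25 if all four partner groups are shown. The drawback is that patients without a pre-palbociclib CBC do not contribute to the worsening rate. They include anyone already on palbociclib at consent with no earlier count recorded, a situation that footnote 8 of Table 1 allows for; the documents do not say how many there are.

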8.9.1 EORTC QLQ-C30

EORTC QLQ-C30 scores and subscores will be summarized at baseline and each post-baseline visit. Paired t-test p-values will be reported. Change from baseline at each post-baseline visit will be summarized if both values are nonmissing. The EORTC QLQ-C30 scores will be compared with country population norms as part of this analysis.

Furthermore, repeated-measures models with unstructured covariance may be considered to estimate average change in global health status (as measured by the EORTC QLQ-C30) from baseline at each post-baseline timepoint. If such models will be performed, time from baseline will be included as a categorical covariate. For each outcome measure, model-based predicted values (least squares means) may be presented along with 95% CIs for each time point.

A descriptive analysis of EORTC QLQ-C30 scores and subscores will be conducted by the following categorizations: age at baseline, LOT, ECOG performance status, any dose modifications, and by SAE status. Two-sample t-test p-values will be reported for category comparisions.

PFIZER CONFIDENTIAL

In addition, differences in EORTC QLQ-C30 “worsening” (see definition in Appendix 1 Derived Data Details) percentages between categorizations for age at baseline and LOT at post-baseline timepoints. Counts and percentages will be reported along with 95% CIs (based on Wilson’s Score as Modified by Newcombe)¹⁹ and chi-square p-values.

8.9.2 Activities of Daily Living

Activities of Daily Living (ADL) is assessed using a six-item ADL limitations measure that inventoried whether participants had difficulty bathing, dressing, toileting, feeding, with transfer, and incontinence.^{20, 21} Respondents selected 1 (unable to do without assistance), 2 (partial assistance needed), or 3 (no assistance).

For each of the 6 activities, counts and percentages will be reported by response at baseline and each post-baseline timepoint. In addition, a summary score using Katz Index will also be presented.

Change from baseline in total score at each post-baseline visit will be summarized if both values are nonmissing. Furthermore, repeated-measures models with unstructured covariance may be considered to estimate average change in ADL summary score from baseline at each post-baseline timepoint. If performed, the model with time since baseline will be included as a categorical covariate. For each outcome measure, model-based predicted values (least squares means) may be presented along with 95% CIs for each time point.

ADL binary categorizations may be paired at baseline and each post-baseline timepoint and, if performed, p-values based on McNemar’s test will be reported.

8.9.3 G8 Screening Tool

Physician responses to the G8 items and index score will be summarized at baseline and each post-baseline timepoint.

G8 binary categorizations may be paired at baseline and each post-baseline timepoint, and, if performed, p-values based on McNemar’s test will be reported.

Change in index score from baseline at each post-baseline visit will be summarized if both values are nonmissing. Furthermore, repeated-measures models with unstructured covariance may be considered to estimate average change in G8 index score from baseline at each post-baseline timepoint. If so, time from baseline will be included as a categorical covariate. For each outcome measure, model-based predicted values (least squares means) may be presented along with 95% CIs for each time point.

8.9.4 ECOG Performance Status

ECOG Performance Status will be summarized by any dose modification category and SAE status.

Categorized ECOG performance status will be examined with ADL category and G8 category at baseline and each post-baseline timepoint. Along with frequencies and percentages, Fisher's exact test p-value will be reported. Furthermore, ECOG performance status may be examined with ADL total score and G8 index score using Pearson correlation coefficients and Spearman's rank coefficients at baseline and each post-baseline timepoint..

CCI [REDACTED]

[REDACTED]

8.9.6 Neutropenia/Lab monitoring pattern

An agreed upon Documentation for Planned Analysis (DPA) will detail the expected analyses prior to execution. Appropriate statistical methodology will be applied to the analyses.

Both Neutropenia and Lab Monitoring Patterns are exploratory analyses to be conducted to explore emerging patterns. The primary exploration will focus on the timepoints during treatment with palbociclib overall and by LOT, evaluated by treatment partner.

In addition to neutrophil counts, palbociclib dosing, palbociclib dose adjustment, MD reported AE of interest, and xx% neutropenia, neutrophil count decrease, by grade; Neutropenia analysis for trend identification between the following will be assessed:

- Correlations of neutropenia value and grade to dosing and dose adjustment
- Neutropenia grades(1/2 vs 3/4) and median by LOT
- Neutropenia grades and median and clinical outcomes: rwPFS
- Neutrophil mean, median, during 1st month, 3 months, 6 months, 12 months, 18 months, 24 months, 36 months, ...

Lab monitoring pattern analysis will include CBC lab testing frequency over palbociclib treatment course, xx% for neutropenia at predetermined time points.

APPENDICES

